13.1.2. Determination of Sample Size

The following assumptions were used in sample size calculations:

- Exponential survival curves, placebo survival estimate of 0.6 at 8 years with a hazard ratio of 0.60, and total study duration of 10 years (from first subject enrolled), allowing for 4 years subject accrual and 6 years of follow up.
- Subjects will be randomized in a 1:1 ratio to placebo or OCA.
- The 2 groups will be compared using a 2-sided log rank test at the 5% level of significance.
- Two interim analyses and one final analysis are planned.

Based on the randomization ratio, significance level, and assumed hazard ratio, a total of 127 events (both groups combined) will provide 80% power to demonstrate a statistically significant difference between OCA and placebo on time to liver-related outcomes, including all-cause mortality.

In addition, based on the remaining assumptions stated above, it is estimated that approximately 428 subjects will be enrolled to attain 127 events.

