Sensitivity analyses will be conducted limiting to the separate individual historical control databases, ie, UK-PBC Group and Global PBC Study Group. To evaluate the robustness of the propensity score estimations, additional algorithms and factors may be considered.

Although the study is designed as a placebo-controlled study, the DMC may recommend changes to study conduct based on the pre-specified interim analyses (see [Section 13.1.12](#)), including the potential use of a revised primary efficacy analysis. This analysis would compare all subjects in the OCA population, to all control subjects (randomized placebo and historical controls) on time to liver transplant or death (all-cause), using similar statistical methodology as specified above.

Notably, the planned primary analysis would not be revised without prior agreement with regulatory authorities.

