13.1.12. Continuous Monitoring and Interim Analyses

Blinded safety reports including the accrual of events, drop outs and/or loss of patients to commercially available OCA will be reviewed by the DMC on a regular basis.

Two planned interim analyses of the liver-related outcomes will be conducted using the Lan-DeMets O'Brien-Fleming boundaries ([Reboussin 2000](#)). Both interim analyses will be pre-specified and will occur after accrual of 50% and 75% of clinical outcome events, respectively.

The DMC will review the available efficacy data in conjunction with detailed safety data and other relevant information to recommend continuation, modification, or cessation (for efficacy or futility) of the study beyond each interim analysis. Modification of the study would not take place without prior agreement with regulatory authorities.

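### Section 13.1.8 (Version 3.1) lets the DMC recommend, after the interim analyses, a new primary endpoint and a partly historical comparator, with nothing in the protocol that would hold the 5% error rate for the revised test

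*Protocol*

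**What the plan says.** The planned primary analysis (Section 13.1.3) compares OCA with randomized placebo on time to the first adjudicated composite event, in the ITT population, by stratified log-rank test. Section 13.1.12 adds two interim analyses, at 50% and 75% of events, with Lan-DeMets O'Brien-Fleming boundaries. At each one, "The DMC will review the available efficacy data in conjunction with detailed safety data and other relevant information to recommend continuation, modification, or cessation".

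Section 13.1.8, which is headed as supportive analysis, then goes further. It says "the DMC may recommend changes to study conduct based on the pre-specified interim analyses", "including the potential use of a revised primary efficacy analysis". The revised analysis is described: "This analysis would compare all subjects in the OCA population, to all control subjects (randomized placebo and historical controls"), on time to transplant or all-cause death, with methods similar to the propensity-score comparison in the same section. The next sentence makes any revision of the primary analysis conditional on prior agreement with regulators, and Section 13.1.12 says the same of any modification of the study.

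Two other places bear on this. Section 13.1.10 states that the sequential procedure maintains the study-wise type I error; that procedure lists only comparisons of OCA with placebo. Section 5.5.2.3 says that historical comparisons support the placebo comparison and that the two are assessed separately.

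**The concern.** The recommendation would come from the body that has just reviewed comparative results on the same subjects, and it would change endpoint and comparator together. No trigger is stated, and the error-control statement in Section 13.1.10 cannot extend to a test that is not in its hierarchy. Pooling historical with placebo controls as primary also conflicts with the supportive, separate role that Section 5.5.2.3 gives them.

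Section 5.5.1 says the study is meant to confirm clinical benefit after a Phase 3 trial based on a surrogate. Section 5.5.2.3 names commercial OCA use as a possible bias in the placebo comparison. A change of analysis would therefore be most attractive when the randomized result looks weak. A positive result after such a change would be hard to read as confirmation.

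**Working it through.** **1. The plan's own figures.** Inputs from Section 13.1.2: "The 2 groups will be compared using a 2-sided log rank test at the 5% level of significance"; "placebo survival estimate of 0.6 at 8 years with a hazard ratio of 0.60"; "Subjects will be randomized in a 1:1 ratio to placebo or OCA"; "a total of 127 events (both groups combined) will provide 80% power". Accrual is 4 years and follow-up 6 years. The 10% dropout is stated in the Version 4 synopsis.

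- Events (Freedman): (1.960 + 0.842)² × [(1 + 0.6)/(1 − 0.6)]² = 7.849 × 16 = 125.6, so 126 against the stated 127. Schoenfeld gives 4 × 7.849/(ln 0.6)² = 120.3, so 121.
- Subjects: hazards are −ln(0.6)/8 = 0.0639 on placebo and 0.6 × 0.0639 = 0.0383 on OCA. P(event) = 1 − [exp(−6λ) − exp(−10λ)]/(4λ) = 0.398 and 0.263, mean 0.331. Then 127/0.331 = 384, and 384/0.9 = 427 against the stated 428.

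The base design is consistent.

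**2. The planned boundary.** Cumulative one-sided spending is 2[1 − Φ(2.241/√t)] = 0.0015, 0.0096 and 0.025 at t = 0.5, 0.75 and 1. The critical values are z = 2.963, 2.359 and 2.014. With no change of analysis, the simulated one-sided error is 0.025.

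**3. Error if the option is used.** The protocol gives no switch rule, so these inputs are assumptions:

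- no OCA effect against placebo;
- correlation 0.55 between the composite and the revised statistic;
- switch at the 75% look, with the revised test judged at 2.014;
- historical bias favouring OCA of 0, 0.5 or 1 standard error of the revised statistic.

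Rule A switches whenever the revised statistic is the larger. Rule B switches only if, in addition, the interim composite z is below 1. The reference column is a pooled test fixed in advance, with no interim choice: error = 1 − Φ(2.014 − bias). There were 1,000,000 simulated paths per setting.

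| Bias (SE) | Pooled test fixed in advance | Rule B | Rule A |
|---|---|---|---|
| 0 | 1 − Φ(2.014) = 0.022 | 0.034 | 0.041 |
| 0.5 | 1 − Φ(1.514) = 0.065 | 0.059 | 0.078 |
| 1 | 1 − Φ(1.014) = 0.155 | 0.12 | 0.161 |

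**4. Where the rise comes from.** With no bias, the increase from 0.025 to between 0.034 and 0.041 is due to the interim choice alone. With bias, Rule A exceeds the fixed pooled test by only 0.078 − 0.065 = 0.013 and 0.161 − 0.155 = 0.006. Rule B falls below the fixed test, because it switches less often. The large figures are therefore mainly the cost of the non-randomized comparator.

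**5. The same check on a hazard scale.** The assumptions here are that transplant or death makes up 30% to 70% of composite events, that 100 to 1,000 historical events are usable, and that the switch is at either look. There were 300,000 runs per setting.

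| Historical hazard above placebo | Rule B | Rule A |
|---|---|---|
| 0% | 0.032–0.037 | 0.037–0.042 |
| 10% | 0.045–0.067 | 0.060–0.089 |
| 25% | 0.093–0.21 | 0.11–0.27 |
| 50% | 0.21–0.58 | 0.26–0.70 |

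**The case against.** **This is a recommendation, not a switch rule.** Nothing changes without regulatory agreement, and the randomized composite remains the default. That stands. A reader might infer that the plan as written has already lost control of type I error. It has not: the 0.025 is intact unless the option is taken up.

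**The alternative is named in advance, and its endpoint is already a key secondary.** This limits the freedom to choose an endpoint. The comparator still changes, and no error rule is tied to the choice.

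**Details of alpha belong in a later amendment or the SAP.** The absence of such detail is not the fault raised here. The protocol itself grants an interim-based option that its own error-control statement does not cover.

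**The DMC may not be unblinded.** Section 13.3 describes closed-session tables with dummy-labelled arm columns and unblinding of individual subjects as needed. The justification column of Appendix G speaks of DMC recommendations following review of blinded data. Full unblinding is therefore an inference and should not be stated as fact. However, efficacy boundaries need results by arm, and choosing between analyses on by-arm results inflates error whatever the column labels. I take Appendix G as evidence of the sponsor's intent, not as a contradiction.

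**The version.** Section 13.1.8 as quoted is Version 3.1 text. Version 4 begins later in the same file, and its synopsis shows changes to the statistics, but its Section 13.1.8 is not shown. This stands and lowers confidence.

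**Conclusion.** The concern holds in limited form. Version 3.1 permits an interim-based recommendation to change both primary endpoint and comparator, and nothing in the protocol preserves the 5% level for the revised test. Regulatory agreement is a procedural safeguard and does not restore the error rate.

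If the option is used under the assumed rules, the one-sided error is about 0.034 to 0.041 with exchangeable historical controls. It is about 0.06 to 0.08 with bias of 0.5 standard errors towards OCA, and 0.12 to 0.16 with 1. These figures rest on the assumed correlation, switch rules, critical value and bias, none of which the protocol states. Bias in the opposite direction would lower them. A reader might take 0.16 as the cost of the interim choice, but the fixed-test comparison shows that most of it is historical-control bias.

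Should-fix, with medium confidence because the Version 4 text cannot be checked.

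**What to change.** Reword the two sentences in Section 13.1.8 that introduce and describe the revised primary analysis. State that the randomized ITT comparison of the composite remains the confirmatory primary analysis at its planned alpha whatever the interim shows, and that the pooled historical comparison is supportive only. This matches Section 5.5.2.3.

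If the sponsor wants to keep room for redesign, limit the trigger to blinded pooled quantities: event count, retention and commercial OCA uptake. Sections 13.1.2.1 and 13.1.12 already provide for blinded monitoring of these, and the Appendix G rationale points the same way. The decision should rest with people who have no access to closed DMC reports.

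The cost is a rewording and no new data. The sponsor gives up an unblinded fallback; one with a blinded trigger remains possible by amendment. Before acting, check whether Section 13.1.8 of Version 4 still contains the option.

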13.1.9. Handling of Dropouts or Missing Data

Subjects who discontinue investigational product are expected to continue in the study until study termination.

Missing data will be assumed to be missing at random. In order to determine the effect of missing data on the analysis, efficacy endpoints will be analyzed using different methods of imputation as described below.

13.1.9.1. Time to Event Endpoints

For the time to event analyses, subjects who do not experience an event will be censored at the time of their last contact. Subjects with no data after randomization will be considered to have an event on Day 1 (first day of investigational product dosing).

For analyses of the percentage of subjects with an event, subjects with no data after randomization will be considered to have an event.

All time to event endpoints include only adjudicated events. Sensitivity analyses may consider all events regardless of adjudication. Events with discrepant adjudication will be analyzed using both results.

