8.4.3. Other Reasons for Discontinuation of Study or Investigational Product

Subjects who discontinue investigational product are expected to continue in the study until the end of the study or at the discretion of the Sponsor. With the exception of liver transplant, if a subject experiences a suspected or confirmed clinical outcomes event, he or she should continue the regular visit schedule and continue taking investigational product as long as the Investigator assesses it as safe. Subjects who discontinue investigational product prior to termination of the study need to also continue to follow the regular visit schedule through to study closure. In general, subjects should be strongly encouraged to both stay on investigational product and remain in the study until study termination. Early termination procedures should only be conducted if the subject withdraws consent (See [Section 9.7.18](#)).

The following events are considered appropriate reasons for a subject to discontinue investigational product; however, these subjects are expected to continue in the study until study termination (or at the discretion of the Sponsor):

- Subject begins treatment with commercially available OCA
- The Investigator or Sponsor considers that it is advisable or in the best interest of the subject.
- The occurrence of clinical or laboratory AEs considered by the Investigator to be clinically important safety concerns and related to study drug.
- Withdrawal of consent
 - Consent may be fully withdrawn (in which case the subject discontinues both investigational product and study visits and procedures).
 - Consent may be modified to discontinue study visits but allow semi-annual telephone contact.
 - Consent may be modified to discontinue study visits or semi-annual telephone contact but allow continued access to medical records to assess for suspected major adverse cardiovascular events (MACE), liver-related clinical outcomes, and drug-related hepatic injury events.

The Investigator is encouraged to contact the Sponsor prior to discontinuing a subject from treatment. The Investigator must notify the Sponsor study monitor by telephone or email as soon as possible if any subject prematurely withdraws from the study.

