Early Termination	Discontinued	Withdrawn	No additional visits except EOT/EOS	Combined Visit, Completed as close as possible to last dose IP	
Treatment Discontinuation^b	Discontinued	Active	Regular Visit Schedule	Complete as close as possible to last dose IP	Complete at Final study visit
	Discontinued	Semiannual contact ^c	Telephone contact every 6 months (± 2 weeks)	Combined Visit, Completed as close as possible to last dose IP	
	Discontinued	Record review only ^c	Record review only	Combined visit Completed as close as possible to last dose IP	
Sponsor Termination	Discontinued	N/A	No additional visits except EOT/EOS	Combined visit Completed as close as possible to last dose IP	
Pregnancy	Interrupted	Retained	Regular Visit Schedule	Complete as close as possible to last dose IP	Complete at Final study visit
	Discontinued	Complete per the above scenarios - Early Termination or Treatment Discontinuation			
Lost to Follow-up	Discontinued	LTF	None	Unable to complete due to LTF status	

EOS = end of study; EOT = end of treatment; IP = investigational product

^a Refer to [Section 7.1.2](#) Schedule of Study Procedures, [Table 2](#) for all procedures and evaluations required at the End of Treatment and End of Study Visits.

^b Includes initiation of commercially available OCA.

^c Outcomes data to be discussed or collected include data related to adjudicated hepatic and cardiovascular event-related data. No additional data (e.g. AE, concomitant medication, etc) data will be collected, except as indicated in [Section 12.1.7](#).

Some assessments noted below may be omitted if they have been completed within the 6 months (or the timeframe otherwise specified) and so long as safety issues do not warrant repeat testing.

Prior to the EOT/EOS Visit:

If possible to do before the visit, when scheduling the EOT/EOS visit, reiterate dosing instructions and advise the subject:

- If applicable, NOT to take investigational product on the morning of the next visit, and
- To bring the investigational product bottle(s); if applicable, s/he will dose at the clinic, and
- To fast overnight (at least 8 hours) prior to the next visit. Fasting is required prior to all study visits, but water is permitted.

During the EOT/EOS Visit:

- Perform a physical examination (including smoking and alcohol consumption habits).
- Perform assessment for calculation of Mayo Risk Score.
- Perform assessments for calculation of Child-Pugh Score.

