Hematology	Hemoglobin, hematocrit, white blood count with differential, neutrophils, lymphocytes, monocytes, eosinophils, basophils, platelets, red blood cell count (including MCV, MCH, MCHC)
Coagulation	Prothrombin time (PT), partial thromboplastin time (PTT), international normalized ratio (INR)
Urinalysis	pH, specific gravity, total protein, glucose, ketones, bilirubin, blood, microscopic exam, urobilinogen, albumin, creatine, leucocytes, nitrates, albumin/creatinine ratio (if positive)
Biomarkers of Hepatic Fibrosis and/or Inflammation	IgM, C-reactive protein (CRP), TNF- α , FGF-19, CK-18, ELF, and others as determined during course of study
Genetics	DNA including single-nucleotide polymorphisms (SNPs) that may be involved in PBC; RNA
Blood Sample for Future Analysis	PBC autoantibodies and other cytokines and interleukins TBD
Other	OCA (parent and conjugates [glyco and tauro], OCA-glucuronide) and C4

The Investigator should manage subjects with clinically significant lipoprotein abnormalities using local standard of care procedures as appropriate after assessing the individual subject's total cardiovascular risk profile.

Urine-based β -hCG pregnancy tests will be performed in female subjects of childbearing potential per protocol specified visits. If a urine pregnancy test is positive, a serum pregnancy test must be performed to confirm the result. If positive, the Sponsor must be notified and the subject will be followed, as outlined in [Section 12.1.9](#) through pregnancy outcome.

MELD scores, Child-Pugh score, and MRS will be calculated at screening, and at quarterly (MELD and Child-Pugh scores) or semi-annual (MRS) visits based on serum chemistry and coagulation.

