The primary efficacy analysis will compare OCA to placebo with respect to the primary efficacy endpoint using the ITT population. The 2 treatment groups will be compared using the log rank test stratified by the randomization stratification factor. Kaplan Meier (KM) estimates of the distribution of the time-to-event will be tabulated and graphed by treatment group. The tabulation will include the KM estimate of the medians and corresponding 95% confidence intervals (CIs), if the medians can be estimated. The number and percent of subjects censored and with events will be presented. The hazard ratio and its 95% CI will be determined based on a Cox regression model stratified by randomization strata to estimate the magnitude of the effect. The same analyses for primary efficacy endpoints will be performed for PP population as a sensitivity analysis.

Key Secondary Efficacy Analyses

The key secondary efficacy endpoints are as follows:

- Time to first occurrence of MELD score ≥ 15
- Time to liver transplant or death (all-cause)
- Change from Baseline in total bilirubin at end of study
- Change from Baseline in ALP at end of study

The key secondary efficacy analyses will compare OCA to placebo in the ITT population with respect to the key secondary efficacy endpoints. Only adjudicated events will be included in time-to-event analyses. The comparison (hypothesis testing) will be conducted in a sequential closed testing gate-keeping procedure (in the order in which the key secondary endpoints are stated above), provided that the primary efficacy endpoint comparison is statistically significant in favor of the OCA treatment group. If the primary comparison is not statistically significant then comparison of the secondary endpoints will be considered as descriptive and exploratory. The same analyses for key secondary efficacy endpoints will be performed for PP population as a sensitivity analysis.

Additional Secondary Efficacy Analyses

The following time-to-event secondary efficacy analyses will compare OCA versus placebo using the ITT population:

- Time to each component of the primary efficacy endpoint (except MELD score ≥ 15 which is captured above)

- Time to development of varix/varices
- Progression to cirrhosis
- Time to occurrence of HCC
- Time to liver-related death
- Time to liver-related death or liver transplant
- Time to liver-related death, liver transplant, or MELD score ≥ 15

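### Time to MELD ≥15 is censored at last contact, so telephone-only follow-up, which has no scheduled laboratory tests, counts as MELD-free time

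*Protocol*

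**What the plan says.** Section 13.1.9.1 sets the censoring date for all time-to-event endpoints: "For the time to event analyses, subjects who do not experience an event will be censored at the time of their last contact". It makes no exception for endpoints that need a laboratory value. The only sensitivity analyses it names for these endpoints concern adjudication.

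Section 12.2.7 states how MELD is obtained: "MELD scores, Child-Pugh score, and MRS will be calculated at screening, and at quarterly (MELD and Child-Pugh scores) or semi-annual (MRS) visits", from serum chemistry and coagulation.

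Section 8.4.3 offers two routes by which a subject stays in follow-up without visits. The first is "Consent may be modified to discontinue study visits but allow semi-annual telephone contact". The second is "Consent may be modified to discontinue study visits or semi-annual telephone contact but allow continued access to medical records". Table 7 in Section 9.7.18 gives both routes one combined end-of-treatment/end-of-study visit near the last dose. After that comes either "Telephone contact every 6 months (± 2 weeks") or record review alone. Footnote c limits collection to hepatic and cardiovascular event-related data and adds, subject to one safety-reporting exception: "No additional data (e.g. AE, concomitant medication, etc) data will be collected".

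MELD ≥15 is a component of the primary composite (Section 13.1.3). It is also the first key secondary endpoint, "Time to first occurrence of MELD score" ≥15 (Section 13.1.4), and step 2 of the testing sequence (Section 13.1.10). The Version 4 synopsis keeps it in the composite and as first key secondary.

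**The concern.** A censoring date should be the last time at which the event could have been recorded. For death, transplant or a hospital admission, a telephone call can serve. For MELD ≥15 it cannot, because the score needs bilirubin, creatinine and INR. A subject who leaves visits at year 2 and is telephoned until year 8 stays in the MELD risk set for 8 − 2 = 6 years with no scheduled way to register the event. The missing-at-random assumption in Section 13.1.9 does not help, since this time is analysed as observed and event-free.

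The first key secondary endpoint is fully exposed. If one arm has more telephone-only follow-up, its MELD hazard is diluted more and the comparison shifts in that arm's favour.

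Record-review-only subjects raise a different problem. They have neither visits nor calls, and last contact is not defined for them. Event-free subjects may be cut at their last visit while events found later in the records still count.

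**Working it through.** **The plan's own figures.** Section 13.1.2 gives placebo survival 0.60 at 8 years, hazard ratio 0.60, two-sided 5%, 1:1 allocation, 80% power, two interim looks, and 4 years of accrual plus 6 of follow-up.

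- Schoenfeld: 4 × (1.960 + 0.842)² / (ln 0.60)² gives 121 events. Freedman: (1.6/0.4)² × (1.960 + 0.842)² gives 126. With Lan-DeMets O'Brien-Fleming looks at 50% and 75%, power at 127 events is 0.813 (Schoenfeld) or 0.797 (Freedman). The stated 127 is reproduced.
- Placebo hazard: −ln(0.6)/8 = 0.0639 per year. Event probability is 0.398 on placebo and 0.263 on OCA, mean 0.331. Then 127/0.331 = 384, and with the 10% dropout in the Version 4 synopsis, 384/0.9 = 427, against the stated 428.

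**Assumptions not in the documents.** Share moving to remote follow-up by year 8: 10% to 30%, at a constant rate. MELD share of the composite hazard: 30% to 70%. No MELD seen after visits stop. Components independent. Follow-up uniform over 6 to 10 years.

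**Hand check, no true effect.** If a fraction f leaves visits by year 8, the leaving rate is g = −ln(1 − f)/8, and the fraction still on visits at time t is exp(−gt). Under last-contact censoring the observed MELD hazard is roughly the true hazard times that fraction. The apparent hazard ratio at time t is therefore about exp(−(g_OCA − g_placebo)t).

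- 20% OCA, 10% placebo: g = 0.0279 and 0.0132. At year 4 the ratio is exp(−0.0147 × 4) = 0.943. Simulation gives 0.94 to 0.95.
- 30% OCA, 10% placebo: g = 0.0446 and 0.0132. At year 4 the ratio is exp(−0.0314 × 4) = 0.882. Simulation gives 0.88.

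**Simulated hazard ratios (600,000 per arm), last contact against last laboratory test**

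| Setting (remote by year 8) | MELD ≥15, last contact | MELD ≥15, last lab | Composite, last contact |
|---|---|---|---|
| True HR 0.60; 20% in both arms | 0.60–0.61 | 0.60 | 0.60–0.61 |
| True HR 0.60; 30% OCA, 10% placebo | about 0.53 | 0.59–0.60 | 0.55–0.58 |
| True HR 0.60; 10% OCA, 30% placebo | 0.68–0.69 | 0.60–0.61 | 0.62–0.66 |
| No effect; 30% OCA, 10% placebo | 0.88 | 1.00 | 0.94 |
| No effect; 10% OCA, 30% placebo | 1.13 | 1.00 | 1.05 |

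The no-effect rows use a MELD share of 50%; the others span 30% to 70%.

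**Equal departure.** With 10%, 20% or 30% remote in both arms, about 5%, 10% or 16% of composite person-time is unobserved for MELD. At 20%, expected composite events from 428 subjects fall from about 142 to between 132 and 138.

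**The case against.** Several points against the concern have force.

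- **Records can show MELD.** Footnote c allows hepatic event data, record review under Section 8.4.3 looks for liver-related outcomes, and adjudicators may use hospital records (Section 13.4). A reader might infer that MELD ≥15 is unobservable in all remote follow-up. For record-review subjects that is too strong, and if last contact means their last visit, their MELD censoring is already right. If half of the remote MELD events were detected, the 20% against 10% null hazard ratio would be about 0.975.
- **Imbalance is not shown.** A reader might infer that pruritus on OCA, or placebo subjects seeking commercial OCA, will make departure unequal. Sections 7.4.2, 8.4.3 and 9.2.1 keep subjects who stop study drug, including commercial OCA users, on the visit schedule; remote follow-up needs modified consent. At 10% against 5% remote, the null MELD hazard ratio is about 0.97 and the composite 0.98 to 0.985.
- **Type I error.** A reader might infer an inflated error at step 2. MELD is tested only after a significant primary (Section 13.1.10), so a stand-alone rate is not the trial's rate. With no effect and a single final analysis, the chance of passing both steps was 1.7% to 2.2% for 20% against 10%, and 2.0% to 3.6% for 30% against 15%, against a nominal one-sided 2.5%. No error figure is claimed here.
- **The primary endpoint.** A reader might infer that it is compromised. Deaths, transplants and admissions remain detectable. If an unseen MELD ≥15 leads to such an event at an assumed 0.3 per year, the null composite hazard ratio for 30% against 15% is 0.97 to 0.98.
- **Leave it to the SAP.** Section 13 defers analysis detail to a SAP. But this rule is stated in the protocol, not left open.

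The first four points limit the size and reach of the problem. None removes it for telephone-only subjects on the MELD endpoint.

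**Conclusion.** The rule is wrong as written for time to MELD ≥15 in subjects followed only by telephone, and it touches the primary composite to a lesser degree through its MELD component. With equal departure the treatment comparison is about unbiased; the harm is lost events and Kaplan-Meier curves that are too favourable in both arms. With unequal departure the hazard ratio is biased in favour of the arm with more remote follow-up: about 0.94 to 0.95 instead of 1.00 for MELD at 20% against 10%, with a smaller shift in the composite. These sizes rest on assumed departure rates, an assumed MELD share, and no MELD detection after visits stop.

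For record-review-only subjects the defect is an undefined censoring date. All of this concerns the Version 3.1 text. Version 4 lists Section 13.1.9.1 in its contents, but the section itself is not shown, so whether the rule persists is unknown.

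**What to change.** First confirm whether Version 4 keeps the rule. If it does, amend Section 13.1.9.1 before unblinding:

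1. Censor time to MELD ≥15 at the last date on which MELD could be calculated.
2. For the primary composite, keep clinical events found after visits stop, and add a sensitivity analysis that censors at the last MELD-evaluable date.
3. For record-review-only subjects, define the censoring date as the last record-review date for components that records can show.
4. State, in Table 7 footnote c, that dated local bilirubin, creatinine and INR values in reviewed records may be used to derive MELD.

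This costs some wording and one footnote, with no new visits. The downside is slightly fewer MELD person-years, and censoring when visits stop may itself be informative. If the whole composite were censored at the last laboratory test, as in the sensitivity analysis, expected events with 20% remote in each arm would be about 128, against 132 to 138 under the current rule.
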